4 Department of Critical Care, Université de Sherbrooke, Sherbrooke, Québec, Canada

5 Interdepartmental Division of Critical Care, University of Toronto, Toronto, Ontario, Canada

6 Department of Health Research Methods, Evidence and Impact, the Research Institute of St Joseph's Healthcare, Hamilton, Ontario, Canada

7 Departments of Medicine, Health Research Methods, Evidence and Impact, McMaster University, Hamilton, Ontario, Canada

Correspondence: [name], Departments of Medicine & Health Research Methods, Evidence and Impact, McMaster University Health Sciences Center, [name]; [contact]

Key Words: upper gastrointestinal bleeding, critically ill patient, risk factors, competing events

Word Count: 2051

Abstract Word Count: 262

REVISE: Clinical Trial Registration: www.clinicaltrials.gov NCT03374800

Abstract

Background: While studies have reported risk factors for clinically-important upper gastrointestinal bleeding among critically ill patients, the risk factors for patient-important upper gastrointestinal bleeding, as defined by ICU survivors and family members, are unknown. Further, although trials show that stress ulcer prophylaxis with pantoprazole decreases the risk of upper gastrointestinal bleeding, some research suggests that mortality may be increased among patients with high illness severity who are exposed to pantoprazole. The risk of death during critical illness is greater than the risk of upper gastrointestinal bleeding.

Objective: To identify risk factors for patient-important upper gastrointestinal bleeding among invasively ventilated critically ill adults, taking into account illness severity and the competing risk of death.

Materials and Methods: This pre-planned secondary analysis of the REVISE trial database will be guided by this protocol. We will use Cox proportional hazards regression analysis to assess the effect of candidate risk factors on the hazard rate of the primary outcome of time to patient-important upper gastrointestinal bleeding, considering the competing risk of death. We propose 2 sensitivity analyses. Secondary analyses will evaluate risk factors for clinically-important upper gastrointestinal bleeding, and another model will evaluate whether enteral nutrition attenuates the effect of pantoprazole on bleeding prevention compared to placebo by including an interaction term between pantoprazole vs. placebo and amount of enteral nutrition received.

Results: This study will identify conditions of critical illness which confer an increased risk of patient-important upper gastrointestinal bleeding in critically ill patients, and factors that decrease the risk.

Conclusions: The findings may inform bedside care, practice guidelines, and the design of future studies.

Introduction

Patients and other members of the public infrequently have input into research priorities, protocol design and study conduct [1]. It has been suggested that patient input is inadequate for outcome selection in many trials conducted in general [2,3] and critical care medicine [4]. Historically, large multicenter trials evaluating upper gastrointestinal bleeding as a complication of critical illness have been focused on the outcome of clinically-important upper gastrointestinal bleeding - an endpoint defined by clinician-researchers [5-9]. In collaboration with survivors of critical illness and family members of patients who were admitted to an intensive care unit (ICU), an outcome of patient-important upper gastrointestinal bleeding was recently developed [10].

This outcome of patient-important bleeding was a secondary endpoint for a recent stress ulcer prophylaxis trial [11]. REVISE (Re-Evaluating the Inhibition of Stress Erosions) was an international, parallel group randomized clinical trial that included 4,821 patients to test the effect of pantoprazole versus placebo on the primary efficacy outcome of clinically-important upper GI bleeding and the primary safety outcome of 90-day mortality [12,13]. Pantoprazole reduced both patient-important and clinically-important upper gastrointestinal bleeding (hazard ratio [HR] 0.36; 95% CI 0.25 to 0.53; $p<0.001$, and HR 0.30; 95% CI 0.19 to 0.47; $p<0.001$, respectively), without affecting other endpoints [11].

In REVISE, patient-important upper gastrointestinal bleeding occurred more frequently than clinically-important upper gastrointestinal bleeding. While studies have reported risk factors for clinically-important upper gastrointestinal bleeding [14], the risk factors for patient-important upper gastrointestinal bleeding, as defined by ICU survivors and family members, remain unknown. While some bleeding events confer an increased risk of death [15], most bleeding ICU patients do not die with or from gastrointestinal bleeding [11]. Dying is nonetheless a competing risk for bleeding, and dying is more common than bleeding. Thus, the primary objective of the current study is to identify risk factors for patient-important upper gastrointestinal bleeding among invasively ventilated critically ill adults, taking into account illness severity and the competing risk of death.

Materials and Methods

Risk Factor Analysis

This pre-planned secondary analysis of the REVISE trial data will be guided by this protocol. The inception cohort will comprise the 4,821 participants in the REVISE trial. These were critically ill patients who were receiving invasive mechanical ventilation patients in the ICU, who were expected to remain ventilated beyond the calendar day after randomization, and were without a clear indication or contraindication to pantoprazole [12,13].

We will use Cox proportional hazards regression analysis to assess the effect of candidate risk factors on the hazard rate of the primary outcome of time to patient-important upper gastrointestinal bleeding, considering the competing risk of death [16,17]. In REVISE, approximately 10 times as many patients died at 90-days than experienced upper gastrointestinal bleeding. The main analysis will then be a competing risk analysis for the competing risk of death [18]. The proportional hazards assumption (which states that the effects of the time-dependent variables remain stable over time) will be assessed and handled appropriately using time-varying effects [19]; alternative methods will be used if this is not satisfactory [20]. We will also assess collinearity of the independent variables (e.g., therapeutic anticoagulation and coagulopathy).

We will include both baseline variables and time-dependent variables, described further below. All time-dependent risk factors will be defined as existing any time in the preceding 3 days, but not including the day of bleed. For bleeds that occur on day 1 of the study, we will use day 1 data to define the time-dependent covariates. We will consider ICU discharge and consent withdrawal as censoring events.

Dependent Variables:

Primary Outcome

The primary dependent variable will be patient-important upper gastrointestinal bleeding. This was defined in a mixed-methods study of ICU survivors and families [21], with gastrointestinal bleeding judged as important if bleeding resulted in a blood transfusion, vasopressor treatment, diagnostic endoscopy, CT-angiography, surgery, or if it resulted in death, disability, or prolonged hospitalization [10]. These criteria were applied to the REVISE database up to 90 days after randomization [11]. Our main analysis will include all patient-important upper gastrointestinal bleeds that occurred in the ICU.

Among 4,821 patients, 136 (2.8%) had patient-important upper gastrointestinal bleeding, 5 of whom bled on the ward prompting ICU readmission. These 5 patients will be censored at ICU discharge, as daily data for the time-dependent risk factors were not collected beyond the index ICU admission.

Secondary Outcome

A secondary analysis will be to determine risk factors for the secondary outcome of clinically-important upper gastrointestinal bleeding. We defined clinically-important upper gastrointestinal bleeding as the presence of overt bleeding (hematemesis, overt nasogastric bleeding, melena, or hematochezia) and at least one of the following within 24 hours in the absence of another cause: spontaneous decrease in invasively monitored mean arterial pressure or non-invasive systolic or diastolic blood pressure of 20 mmHg or more or an orthostatic increase in pulse rate of 20 beats/minute and a decrease in systolic blood pressure of 10 mmHg, with or without vasopressor initiation or increase; vasopressor initiation; a decrease in hemoglobin of ≥ 20 g/L in a 24-hour period or less; transfusion of ≥ 2 units of packed red blood cells within 24 hours of bleeding, or therapeutic intervention (e.g., angio-embolization, surgery or endoscopic treatment of bleeding) [12]. Each bleed was reviewed in duplicate by an adjudication committee, blinded to study drug, to determine whether the clinically-important upper gastrointestinal bleeding criteria were fulfilled [22].

Among 4,821 patients, 109 (2.2%) had an event which were adjudicated as clinically-important upper gastrointestinal bleeding, 5 of whom bled on the ward prompting ICU readmission. These 5 patients will be censored at ICU discharge, as daily data for the time-dependent risk factors were not collected beyond the index ICU admission.

Independent Variables:

Bleeding risk factors will include both baseline and time-dependent variables. Factors will draw on pathophysiologic rationale and prior literature. Given the number of patient-important upper gastrointestinal bleeds, we have taken into account the suitable number of independent variables to avoid an over-fitted model [23]. The same risk factors will be analyzed for the secondary outcome of clinically-important upper gastrointestinal bleeding as for the primary outcome of patient-important upper gastrointestinal bleeding.

Baseline Variables

- 1) APACHE II score (considered as a continuous variable)
- 2) Medical vs. surgical/trauma (considered as 2 categories)
- 3) Pantoprazole versus placebo as randomized (considered as 2 categories)

Time-dependent Variables

- 1) Respiratory failure, defined as receiving invasive mechanical ventilation (considered as 2 categories)
- 2) Circulatory failure, defined as receiving inotropes or vasopressors (any dose of any of norepinephrine, epinephrine, phenylephrine, vasopressin, dopamine, dobutamine or milrinone) (considered as 2 categories)
- 3) Renal failure including acute kidney injury or end-stage renal disease, defined as receiving renal replacement therapy (any of intermittent hemodialysis [IHD], continuous renal replacement therapy [CRRT], sustained low efficiency dialysis [SLED] or peritoneal dialysis) (considered as 2 categories)
- 4) Enteral nutrition in mL/day (considered as a continuous variable)

- 5) Therapeutic anticoagulation, defined as therapeutic unfractionated heparin or low molecular weight heparin, fondaparinux, warfarin, non-vitamin K antagonist oral anticoagulants including anti-Xa inhibitors and direct thrombin inhibitors, and thrombolytic therapy (considered as 2 categories)
- 6) Coagulopathy, defined as international normalized ratio (INR) > 3.0 or prothrombin time (PTT) > 70 seconds (considered as 2 categories)
- 7) Severe thrombocytopenia, defined as platelet count $< 50 \times 10^9/L$ (considered as 2 categories)
- 8) Platelet aggregation inhibitors, defined as receipt of any of acetyl salicylic acid, clopidogrel, dipyridamole, ticlopidine, tirofiban, P2Y12 inhibitors, or non-steroidal anti-inflammatory drugs (considered as 2 categories)
- 9) Corticosteroids, defined as any corticosteroid drug or dose, either enteral or intravenous administration (considered as 2 categories)

Sensitivity Analyses

- 1) To evaluate the effect of the competing risk of death, we will conduct an analysis that does not consider the competing risk of death.
- 2) To evaluate the influence of risk factors more proximate to the bleed, we will evaluate all time-dependent risk factors defined as any time in the preceding 2 days, instead of the preceding 3 days.

Secondary Analyses

- 1) To evaluate risk factors for clinically-important upper gastrointestinal bleeding, we will repeat the same analysis [11].
- 2) To evaluate whether enteral nutrition attenuates the effect of pantoprazole on bleeding prevention compared to placebo, we will include an interaction term between pantoprazole vs. placebo and amount of enteral nutrition received [24,25].
- 3) To evaluate whether certain baseline conditions are associated with patient-important upper gastrointestinal bleeding, we will include these variables in the main model one at a time: acute hepatic failure [26], traumatic brain injury [27] and female sex [28].

Missing Data

We anticipate little missing data except for 2 risk factors in patients with length of ICU stay greater than 2 weeks. Platelet aggregation inhibitors and corticosteroids were not collected from day 15 onwards 14 on the abbreviated trial case report form. For the primary analysis, if there are any patients remaining in the ICU after 2 weeks who received a platelet aggregation inhibitor on day 14, we will impute that it was continued until ICU discharge, except in the event of bleeding, assuming that the indication persisted over time (e.g., coronary artery disease). For the primary analysis, we will impute that if there are any patients receiving corticosteroid treatment on day 14, it was continued only to day 21, assuming the indication resolved (e.g., septic shock).

Results

We will report independent variables and other characteristics of participants with and without patient-important upper gastrointestinal bleeding using descriptive statistics, including means and standard deviations (or medians with interquartile ranges, if appropriate) for continuous data, and numbers with percentages for categorical data.

Figures we will present include the day of each bleed in the ICU, the concordance between patient-important gastrointestinal bleeding and clinically-important upper gastrointestinal bleeding, and the daily use of invasive ventilation and any enteral nutrition.

Regression results will be presented as adjusted hazard ratios with 95% confidence intervals and corresponding two-tailed p-values for the associations of each independent variable with the primary and secondary outcomes. The criterion for statistical significance will be set at alpha = 0.05. No corrections for multiple testing will be performed because of the exploratory nature of the analyses, but findings will be interpreted in light of confidence intervals and cautiously interpreted.

Discussion

In this study, we will examine baseline and time-dependent risk factors for patient-important upper gastrointestinal bleeding, including the effect of pantoprazole versus placebo. Use of the REVISE trial database will build on risk factor analyses of clinically-important upper gastrointestinal bleeding from prior large trials [25,29].

Strengths of this study include the focus on an outcome developed by ICU survivors and relatives of ICU survivors or decedents. We will minimize the risk of over-fitted regression models caused by evaluation of many admitting diagnoses. Beyond assessing baseline characteristics, we will use Cox models to assess interventions and key laboratory values reflecting events and exposures over the ICU stay. Although proton-pump inhibitors for bleeding prophylaxis do not affect 90-day mortality overall as shown in a recent meta-analysis (RR 0.99 [95% CI, 0.93 to 1.05]) [30], within-trial subgroup analysis suggests a possible heterogeneity of treatment effect based on disease severity. Accordingly, the main analysis will address the competing risk of death and a sensitivity analysis will evaluate whether this impacts the results. In this contemporary database, half of the patients were randomized to no stress ulcer prophylaxis, enabling the evaluation of risk factors with and without stress ulcer prophylaxis. This study will address some issues proposed for future research on this topic [31], including evaluating the volume of enteral nutrition (e.g., trophic versus full feeding) and special populations (e.g., acute hepatic failure). Heterogeneous patients from 68 international centers will increase the generalizability of the results.

Limitations of this study include no information on some uncommon exposures in the REVISE trial (e.g., non-invasive ventilation) and on some rare conditions (e.g., admitting diagnosis of organ transplantation). To focus on events that consume healthcare resources, we will not address overt bleeding, which often resolves; if it evolves into patient-important or clinically-important upper gastrointestinal bleeding, these events will be included in this analysis. This study is not designed to construct or both construct and validate a prediction model, which requires a different design. All analyses such as these are subject to confounding, yielding information on association rather than causation, needing cautious interpretation.

Conclusions

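### Prior vasopressor use can change whether a bleed counts as clinically-important, and possibly as patient-important, so the circulatory-failure hazard ratio is open to definitional bias of unknown size

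*Combined protocol and SAP*

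**What the plan says.** The risk factor (Time-dependent Variables, item 2) is: "Circulatory failure, defined as receiving inotropes or vasopressors (any dose of any of norepinephrine, epinephrine, phenylephrine, vasopressin, dopamine, dobutamine or milrinone".

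The primary outcome (Dependent Variables, Primary Outcome) counts a bleed as patient-important if "bleeding resulted in a blood transfusion, vasopressor treatment, diagnostic endoscopy, CT-angiography, surgery, or if it resulted in death, disability, or prolonged hospitalization". It does not distinguish starting, increasing and continuing a vasopressor.

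The secondary outcome (Secondary Outcome) requires overt bleeding and "at least one of the following within 24 hours in the absence of another cause". The list allows a blood-pressure fall "with or without vasopressor initiation or increase; vasopressor initiation": a qualifying fall counts whatever happens to the vasopressor, and starting one is a criterion in its own right. Hemoglobin fall, transfusion and therapeutic intervention are the other routes.

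Under Independent Variables, "The same risk factors will be analyzed for the secondary outcome" as for the primary. Exposure is any receipt in the preceding 3 days without the day of the bleed, except that day-1 bleeds use day-1 data. The two sensitivity analyses change the handling of death and the length of the exposure window. Neither changes what counts as a bleed.

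**The concern.** Take two patients with the same overt bleed on day 8, neither meeting any other criterion. One has been on a vasopressor since day 6; the other has not, and is started on one because of the bleed. Under the clinically-important definition the second patient has an event. The first cannot meet the initiation criterion and has none. The exposure has changed whether the bleed is counted, through the wording of the outcome and not through the risk of bleeding.

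Lagging the exposure does not cure this. The lag stops a vasopressor given for the bleed from being coded as a cause of it. Here the exposure is correctly dated, and the difficulty is which patients are eligible to meet the criterion. Covariate adjustment does not cure it either.

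At stake is the HR for a named candidate factor, in a study whose stated purpose includes informing bedside care and guidelines. The same factors are modelled on both outcomes, and the vasopressor wording differs between them. A difference between the two circulatory-failure HRs could therefore be taken for a real difference between the outcomes when it comes from the wording.

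**Working it through.** **Event counts in the plan.** Patient-important: 136/4,821 = 2.82% (stated 2.8%), and 136 − 5 ward bleeds = 131 events analysed. Clinically-important: 109/4,821 = 2.26% (stated 2.2%, apparently a rounding slip that does not bear on this point), and 109 − 5 = 104 events analysed. The documents do not say how many of these qualified only through the vasopressor criterion, so everything below on size rests on assumed ranges.

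**Set-up.** Let overt bleeding be equally frequent with and without prior vasopressor use (true HR = 1). Any departure of the apparent HR from 1 is then definitional.

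**Reading A: only a new start counts.** This is the wording of the clinically-important criterion. Define:
- f = share of counted bleeds in unexposed patients that qualify only through the vasopressor criterion (assumed 5% to 30%);
- w = share of exposed patients still on the drug at the bleed (assumed 0.5 to 1, since some are weaned within the window);
- s = share of the affected bleeds that are counted anyway, for example because an increase was accepted (0 to 1).

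Relative to unexposed patients, exposed patients lose f × w × (1 − s) of their counted bleeds:

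apparent HR = 1 − f × w × (1 − s)

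- f = 0.05, w = 0.5, s = 0: 1 − 0.025 = 0.975
- f = 0.10, w = 0.8, s = 0: 1 − 0.08 = 0.92
- f = 0.20, w = 0.8, s = 0.5: 1 − 0.08 = 0.92
- f = 0.30, w = 1, s = 0: 1 − 0.30 = 0.70
- s = 1, any f and w: 1.00

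**Reading B: ongoing treatment can count.** The patient-important criterion could have been applied this way, though the documents do not say that it was. Define:
- p = share of overt bleeds counted in patients without prior use (assumed 0.5 to 0.9);
- g = share of otherwise non-counting bleeds credited to ongoing treatment (assumed 0.1 to 0.5);
- w as above.

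apparent HR = [p + w × g × (1 − p)] / p

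- p = 0.9, w = 0.5, g = 0.1: 0.905/0.9 = 1.006
- p = 0.7, w = 1, g = 0.25: 0.775/0.7 = 1.107
- p = 0.5, w = 1, g = 0.5: 0.75/0.5 = 1.50
- extreme case p = 0.5, w = 1, g = 1: 1.00/0.5 = 2.0

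**Scale.** The plan gives no power calculation. By the Schoenfeld formula with two-sided alpha 0.05, 80% power and an assumed exposure share of 30% to 70%, the detectable HR is about 1.63 to 1.71 with 131 events and 1.73 to 1.82 with 104. Most of the distortions above are smaller than that. They would rarely produce a significant result alone, but they could shift an estimate or open a gap between the two outcomes.

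**What dropping the vasopressor criterion does.** Under Reading A with s = 0, unexposed and exposed patients both keep a share 1 − f of the bleeds counted in unexposed patients, and (1 − f)/(1 − f) = 1. Under Reading B the bleeds credited to ongoing treatment drop out, as do vasopressor-only bleeds in unexposed patients, and the ratio is again 1. Both results assume that meeting the other criteria does not itself depend on vasopressor status.

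**The case against.** The strongest reply is that the overlap is narrow.

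- **Other routes.** A bleed that also brings a qualifying blood-pressure fall, hemoglobin fall, transfusion or intervention counts as clinically-important whatever the vasopressor status. This stands: only vasopressor-only bleeds are affected. The blood-pressure and hemoglobin routes are, however, listed only for the clinically-important outcome.
- **Attribution.** One definition requires the treatment to result from the bleed, and the other excludes other causes. A reader might infer that a patient already treated meets the patient-important criterion simply by staying on the drug. The documents do not support this, because a drug running since before the bleed did not result from it. Whether continuation, increase or only a new start was accepted is not stated.
- **Exposure is not current use.** A patient weaned within the 3-day window can still have an initiation. Inotropes count as exposure but are not named in either outcome criterion. The text does not say whether adding a second agent is an initiation. All of this moves the HR towards 1 and is carried by w and s.
- **Adjudication.** Duplicate review is described, but for the clinically-important criteria and blinded to study drug. It applies the definition as written, so it does not remove the asymmetry.
- **Exploratory purpose.** The plan calls the analyses exploratory and associational, and a formal comparison of HRs between outcomes is not planned. This lowers the stakes. A general caution about confounding does not cover ascertainment that depends on exposure.

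A reader might also infer that one underlying truth must give opposite signals in the two outcomes. An example of that kind can be built only by choosing the shares of vasopressor-only bleeds, and the documents give none.

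**Conclusion.** The point holds in limited form. Vasopressor use is in the risk factor and in both outcome definitions, and no planned analysis separates them.

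For clinically-important bleeding the mechanism follows from the wording and runs downward: an apparent HR of 0.70 to 1.00 when the true HR is 1, with vasopressor-only bleeds assumed to be 5% to 30% of counted bleeds in unexposed patients. For patient-important bleeding an effect is possible, but its direction depends on an application rule that is not given: downward if only new starts counted, little or none if increases were also accepted, and upward (about 1.0 to 1.5 in the assumed ranges) if ongoing treatment was.

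The documents do not support saying that either HR is materially biased, or that the two are biased in opposite directions. The real size could be negligible. It depends on a count that the plan does not report.

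The day-1 rule, under which a vasopressor started for the bleed can be coded as exposure, is a separate same-day overlap. Correcting it would leave the present point untouched.

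**What to change.** Add a third sensitivity analysis, run for each outcome, in which a bleed is an event only if it meets at least one criterion other than the vasopressor criterion. Keep patients whose bleed qualifies solely on vasopressors at risk after that bleed. Censoring them would remove the unexposed patient while the matching exposed patient, whose bleed never counted, stayed in follow-up, and handling would again depend on exposure.

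Report the number of vasopressor-only bleeds by prior vasopressor status, for each outcome. Present the circulatory-failure HR and 95% CI from the main and sensitivity analyses side by side. If a difference between the two outcomes disappears in the sensitivity analysis, do not attribute it to biology. One added sentence should state how the patient-important criterion was applied to patients already on a vasopressor.

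The main analysis and both outcome definitions stay as they are. The cost is one model per outcome and a short SAP addition, assuming that the criteria used to classify each bleed can be retrieved. The statistical cost is precision. If 5% to 30% of all counted events were vasopressor-only (assumed), 131 events would fall to about 124 (131 × 0.95) or 92 (131 × 0.70), and 104 to about 99 or 73. With 12 variables (3 baseline, 9 time-dependent), events per variable would go from 131/12 = 10.9 to between 10.4 and 7.6, and from 104/12 = 8.7 to between 8.2 and 6.1. Confidence intervals on the log scale would widen by about 3% (1/√0.95) to 20% (1/√0.70). The reported count will show where in that range the trial lies.

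### Does reusing all 12 covariates for clinically-important bleeding, with 104 analysable events, leave the secondary model unprotected against over-fitting?

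*Combined protocol and SAP*

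**What the plan says.** Under Independent Variables, the combined protocol and SAP states that, in view of the number of patient-important bleeds, "we have taken into account the suitable number of independent variables to avoid an over-fitted model". It cites a methodological paper on events per variable in proportional hazards regression but gives no numerical threshold. The next sentence carries the whole covariate set over: "The same risk factors will be analyzed for the secondary outcome of clinically-important upper gastrointestinal bleeding as for the primary outcome". Secondary Analyses, item 1, confirms that the analysis is simply repeated.

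The set has 3 baseline and 9 time-dependent variables, each either continuous or in two categories.

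The event counts are given under the two outcome headings. For the primary outcome, "136 (2.8%) had patient-important upper gastrointestinal bleeding, 5 of whom bled on the ward prompting ICU readmission". For the secondary outcome, "109 (2.2%) had an event which were adjudicated as clinically-important upper gastrointestinal bleeding, 5 of whom bled on the ward prompting ICU readmission". In both cases the 5 ward bleeds are censored at ICU discharge.

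Two analyses enlarge the main model. Item 2 of Secondary Analyses adds an interaction between pantoprazole and enteral nutrition. Item 3 adds three baseline conditions singly: "we will include these variables in the main model one at a time: acute hepatic failure" is the first, followed by traumatic brain injury and female sex.

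**The concern.** The plan offers protection against over-fitting and ties it to a single event count. The secondary outcome has about a fifth fewer analysable events and the same number of parameters, and nothing is said about whether the set is still suitable. A reader who holds to the common convention of 10 events per variable (an assumption here, not a figure in the plan) sees the primary model just above that mark and the secondary model below it. Extra parameters for the interaction, an added baseline condition or a time-varying effect push the ratio lower still.

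Some binary exposures may also be uncommon: platelets below 50, the coagulopathy definition and acute hepatic failure. With few exposed bleeds, a hazard ratio can be unstable or have no finite estimate. The plan reports a hazard ratio, interval and p-value for every variable at the 0.05 level without multiplicity correction, so unstable secondary results could be read with the same confidence as the primary ones. The percentage printed for the secondary outcome also does not match its count, which raises doubt about which count was used.

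**Working it through.** **Inputs.** Cohort 4,821 (Risk Factor Analysis). Primary events 136, of which 5 on the ward (Primary Outcome). Secondary events 109, of which 5 on the ward (Secondary Outcome). Covariates 3 + 9 = 12 (Independent Variables), one parameter each if continuous terms are linear.

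**Printed percentages.**
- 136/4,821 = 2.82%, printed as 2.8%: reproduced.
- 109/4,821 = 2.26%, which rounds to 2.3%; the plan prints 2.2%. (104/4,821 = 2.16% would round to 2.2%.)

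**Events per variable** = (events − ward bleeds) / parameters.

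| Model | Events | Parameters | Events per variable |
|---|---|---|---|
| Primary, main | 136 − 5 = 131 | 12 | 10.9 |
| Primary, interaction or one added condition | 131 | 13 | 10.1 |
| Primary, two extra parameters | 131 | 14 | 9.4 |
| Secondary, main | 109 − 5 = 104 | 12 | 8.7 |

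The set meets an assumed threshold of 10 for the primary outcome but not for the secondary. It misses 9 for the secondary outcome as well, and meets 8 for both. The 13-parameter primary models stay above 10; two extra parameters are needed to go below it.

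**Cost in precision.** With the same covariates, standard errors scale with 1/√events: √(131/104) = 1.12, or about 12% larger. For a covariate with 50% prevalence, two-sided 0.05 and 80% power, the detectable hazard ratio is exp[(1.96 + 0.84)/√(events × 0.5 × 0.5)], about 1.63 with 131 events and 1.73 with 104.

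**Rare exposures.** The documents give no prevalences, so these are assumptions. With prevalence p and hazard ratio h, the exposed share of events is roughly ph/(1 − p + ph), and the chance of no exposed event among E is (1 − that share)^E. For p = 1% and h from 2 down to 1:
- E = 131: 7% to 27%
- E = 104: 12% to 35%

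Acute hepatic failure is added only to the patient-important model, so only the 131-event range can apply to it.

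**Does penalisation address the events-per-variable gap?** A logistic approximation was simulated (300 replicates, true hazard ratio 2). It compares the root mean squared error of the log hazard ratio under maximum likelihood and under Firth penalisation.

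| Events | Covariates | Prevalence | Maximum likelihood | Firth |
|---|---|---|---|---|
| 104 | 12 | 2% | 0.57 | 0.48 |
| 104 | 1 | 2% | 0.55 | 0.47 |
| 131 | 12 | 2% | 0.52 | 0.46 |
| 104 | 12 | 10% | 0.252 | 0.245 |
| 104 | 12 | 30% | 0.195 | 0.192 |

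At 2% prevalence the gain is 0.57 − 0.48 = 0.09 with twelve covariates and 0.55 − 0.47 = 0.08 with one (104 events per variable). It shrinks to 0.007 at 10% prevalence and 0.003 at 30%. The gain follows the rarity of the exposure, not the number of covariates, and it is also present at 131 events.

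**The case for a change.** The strongest case for a change is that the plan evidently reasoned from events per variable, since it cites a paper on exactly that, and then applied the result to an outcome for which it was not worked out. Neither analysed count, 131 or 104, is printed, and no fallback is given if a rare exposure has no bleeds. Firth-type penalisation keeps all 12 variables, reduces error under the assumed rare exposures and needs little more than a sentence in the SAP.

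Part of this stands. The justification is not made for the secondary outcome, and it would be helpful to see both counts with their ratios. Sparse exposures may also cause trouble, depending on prevalences that the documents do not give.

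The rest does not carry. The statement on suitable numbers of variables refers only to patient-important bleeds, so the plan makes no such promise for the secondary model. The strength claimed in the Discussion, "We will minimize the risk of over-fitted regression models", goes on to specify over-fitting from examining many admitting diagnoses; it is not a general assurance. Penalising only the secondary and enlarged models would depart from repeating the same analysis and would compare a penalised secondary result with an unpenalised primary one. The main analysis is a competing-risk model with time-dependent covariates, and it has not been shown that the penalised partial likelihood carries over to it.

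**Conclusion.** The facts are right, but no change is needed. The secondary model has 8.7 events per variable against 10.9 for the primary. Whether 8.7 is too few depends on a threshold that the plan does not set: it fails at 9 or 10 and passes at 8. The measurable consequence is standard errors about 12% larger, which the reported intervals will reflect.

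Using one covariate set for both outcomes is a fair trade-off. It gives a like-for-like comparison of risk factors, in an analysis that the plan describes as exploratory, to be read cautiously and not meant to build a prediction model. The analysed counts follow by subtraction from the figures given, and analysts would ordinarily report them. If an exposure proves too sparse to estimate, that will be plain in the output for either outcome. A penalised fit could then be shown as a sensitivity analysis for both outcomes alike, if it suits the competing-risk model.

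Printing 2.2% for 109 of 4,821 is a clerical slip with no bearing on any analysis. These conclusions assume one parameter per covariate. Those on rare exposures also rest on assumed prevalences of 1% to 2% and, for the simulation, on a logistic approximation to the planned model.
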